# **Background/Significance**

#### a. History

The theory of electrical stimulation therapy for pain control has been studied at significant length since it was initially theorized. The theory behind the effectiveness of the use of electrical stimulation for pain was described by Melzack and Wall in 1965 as the gate theory of pain modulation. The gate theory of pain describes how pain simulation can be blocked from reaching the brain by other signals ([1-3]). This theory has provided the bases for pain management with electrical stimulation using different modalities. In the 1950s, the use of intereferential current therapy (IFC), was developed to provide dual current therapy to provide deeper tissue penetration to allow for improved pain relief.

The IFC treatment is a form of electrical therapy that utilizes two simultaneous low frequency electrical stimulations which when they cross interfere with one another resulting in an interference or beat frequency. This beat frequency provides a therapeutic area of relief by blocking painful stimuli at the area of interest. IFC is different from the other electrical treatment modalities used because the cancelation effect allows for establishment of the treatment area to be in the deeper tissues of the body, whereas other electrical modalities can only be used to treat superficial body parts that lie just under the skin. The specific frequency of the signal is patient specific and, therefore, we will plan to have each selected patient establish their correct frequency at the pre-operative visit (see more information regarding the device below). By using these properties of IFC, the hope for results of the treatment for patients in the study will be to reduce swelling and edema and reduce the size and extent of hematoma formation This will improve the quality and speed of recovery from the operation, and secondarily decrease pain and discomfort.

# b. Electrical Stimulation for Pain Relief

In the field of orthopaedic surgery, several studies have compared the use of electrical stimulation therapy for patient pain relief with differing results. Two systematic reviews were done comparing use of transcutaneous electrical nerve stimulation (TENS) as a possible adjunct after total knee arthroplasty (TKA). Both studies found significant improvement of pain scales and active knee range of motion ([4, 5]).

More specifically, IFC therapy has also been compared to both TENS and placebo for pain relief. When compared to TENS for back pain, there are conflicting results. Some studies indicate overall pain improvement but no difference between modalities [6, 7]. Another study

found IFC to be more effective in treating chronic low back pain due to deeper tissue penetration [8].

c. Previous use of the device:

One study conducted by Kerlan-Jobe Orthopaedics clinic in 2001 compared IFC therapy to placebo for post-operative pain, edema and range of motion after ACL reconstruction, meniscectomy or knee chondroplasty. In this randomized, double-blind, placebo controlled prospective study, patients were treated post-operatively with IFC therapy providing therapeutic or placebo electrical stimulation. In that study, all IFC subjects reported significantly less pain and greater range of motion all reviewed time points [9].

# **Objective:**

The main objective of this proposed study is to assess the post-operative short term outcomes of the patients who receive IFC treatment during their post- total knee arthroplasty (TKA) surgery hospital stay. The implications of the study would be improved patient outcome which could result in shorter hospital stay, reduced use of opioid medication, decreased need for manipulation under anesthesia and reduced re-admission rate.

# Study Design:

It will be a prospective, randomized, single-blinded study. The study device will be used for only 2 days during the post-surgery hospital stay. The patients will be followed until their 6 weeks post-op office visit. We aim to finalize the study in 6 months.

Before enrollment into the study: During their pre-operative visit, patients will fill out a short questionnaire (The Pain Catastrophizing Scale, PCS short form) to assess their eligibility for the treatment and create a homogenized group of patients. Inclusion criteria is detailed below. 50 patients who are eligible for the study will be enrolled by written consent. Informed written consent will be obtained by PI ([name]) and the health care professional team ([name] and [name],PA ) during pre-operation office visit.

Once the patient volunteers to enroll to the study, we will establish their patient-specific intensity during their pre-op office visit. We will plan to have patient establish their correct and comfortable intensity before their surgery. The device comes in a carrying case with all the set supplies. At the time of placement, a health care provider will place the pre-packaged sterile electrode roughly 7-10 cm above and below the knee for testing or just above and below the

dressing during on the operated knee. Each set of electrodes will then be connected via a lead wire to the stimulation device.

Establishing the correct and comfortable intensity before operation will be as follows: The stimulation device which has a large power button will be turned on but provide no initial signal intensity. The patient will then be instructed to use the "plus" arrow on the device to slowly increase the signal intensity. The goal is to reach a point of intensity that feels strong but comfortable. The best method is to continue to increase to the point where it becomes slightly uncomfortable and the patient may experience some muscle fasciculations. Once that point is reached, decrease the intensity slightly and then use that intensity for their treatment. This patient specific intensity will be recorded and used for the IFC treatment.

Enrolled patients will be randomly assigned to either **i. IFC treatment or ii. Placebo group** after their surgery. Patients in both groups will continue their regular standard post-operative care in addition to the IFC (or placebo) treatment. In addition to their post-operative standard of care, both groups will receive IFC treatment (or Placebo treatment) two times a day, for two days during their post-op hospital stay.

i. For the IFC treatment group: In addition to their post-operative standard of care, the IFC group will receive IFC treatment two times a day, for two days during their post-op hospital stay. The specific intensity of the IFC signal is patient specific. We will use previously established intensity values for each patient.

Once the intensity is set the program will lock automatically after 1 minute of inactivity or can be manually locked using the "star" button on the device. There is some degree of subjectivity in this portion but that is what provides the user with a patient specific signal. The signal intensity can go up to "100" on the device. The device works for 30 minutes at a time. On the device there is a timer which shows the time and it will automatically turn itself off after 30 minutes. During the time when the device is working, the patient can do any regular activity such as ambulating, physical therapy or sleep without concern.

The electrode has an adhesive pad that can remain on the patient post-operatively if desired or can be removed and replaced for each treatment session. The individual electrodes are re-usable and will be assigned to each patient.

For Placebo group: The standard of care and their physical therapy will not be altered for the placebo group. One set of the devices are programmed to be the placebo devices. The placebo devices can give a sensory stimulus so that the patient will feel the device is being on, but they will not have the therapeutic stimulus. We will monitor and record the same post-surgery outcomes as for the treatment group.

The outcomes will be monitored in the immediate post-operative period by the Orthopaedic Surgery clinical team at Wakefield Hospital as well as at during the first post-op visit by [name] office by physician assistant ([name],PA) and nurse practitioner ([name]). The average hospital stay for TKA patients in the hospital (Wakefield) varies between 48-72 hours post-operatively. Typically, patients have a follow-up visit at 2 weeks and 6 weeks after surgery in the Hutchinson Campus, Tower 1 Orthopaedic Surgery Department clinic.

1. Primary outcome will be the post-operative pain medication usage during the first 24 and 48 hours. Daily opioid use will also be accounted based on electronic medical record reported by the patient's nurse after providing the patient with the specific medication. In addition, patients will be asked to rate their pain based on a set VAS pain scale twice a day before the IFC treatment.

2. Secondary outcomes Fitness for discharge on postoperative day 1and day 2 this will be measured utilizing the AM-PAC "6-Clicks" Basic Mobility Inpatient Short Form. The "6-Clicks" tool measures functional ability by having an assessor rate a patient's ability to perform physical tasks such as turning over in bed, moving from a bed to chair, and climbing steps. Scores are tallied to a total of 24 possible points, giving a quantitative measure of a patient's ability to perform these tasks. We will also use the `time` to reach the discharge as the outcome, pain scores recorded by nursing and physical therapy, complications, and any 30-day post discharge emergency department ED visits. Range of motion will be recorded during the daily physical therapy sessions by PT professionals with a goniometer. Range of motion then be assessed again in clinic at the first post-operative visit. Edema- thigh circumference will be calculated at the superior pole of the patella both prior to the surgery and daily post-operatively.All these outcome scores are done routinely as standard of care and they are recorded in patients charts in EPIC.

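### Envelopes that name the arm and an uncoded placebo device set reveal the allocation to staff, and no masking is described for those who give and record opioids

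*Combined protocol and SAP*

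**What the plan says.** Study Design labels the trial: "It will be a prospective, randomized, single-blinded study". It does not say who is blinded.

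All enrolled patients titrate before surgery: "Once the patient volunteers to enroll to the study, we will establish their patient-specific intensity during their pre-op office visit". They are told to "continue to increase to the point where it becomes slightly uncomfortable and the patient may experience some muscle fasciculations", and then to step down slightly. Both Study Design and Randomization place allocation after surgery.

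Study Design then describes the two arms. Under the IFC group: "We will use previously established intensity values for each patient" and "Once the intensity is set the program will lock automatically after 1 minute of inactivity". The 30-minute run time appears there too. Under the placebo group: "One set of the devices are programmed to be the placebo devices" and "The placebo devices can give a sensory stimulus so that the patient will feel the device is being on". The placebo text gives no setting and no run time.

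Randomization has the statistician prepare sequentially numbered envelopes, each containing the arm. Study staff assign them, and the investigator who evaluates patients after surgery is excluded from that task. The primary outcome text in Study Design takes opioid use from the record made by the patient's nurse after giving the drug, and asks patients to rate pain on a VAS. The secondary outcomes include pain scores recorded by nursing and physical therapy, an assessor-rated mobility score, and range of motion measured by physical therapists.

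**The concern.** The envelope tells whoever acts on it which arm the patient is in, and that person must then pick a device from the active or the placebo set. From that moment some of the staff know the allocation. The protocol does not say whether they are separate from the ward nurses and therapists, or whether the devices can be told apart.

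The outcomes are open to influence. Opioid use depends partly on what the patient asks for and what the nurse gives, and VAS pain is the patient's own rating. A cue reaching either person could move these outcomes without any effect of the current. The bias could go in either direction, and it cannot be repaired once the data are collected.

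**Working it through.** **1. The plan's only design figure.** Power/sample size gives a control mean of 84.2 mg, SD 44.7, a 30% reduction, two-sided 0.05 and 80% power. The target is 0.30 × 84.2 = 25.26 mg. By the normal approximation, n = 2 × (1.960 + 0.842)² × 44.7² / 25.26² ≈ 49.2, so 50 per group, as stated. The blinding point does not depend on this figure; it supplies the mean and SD used in step 5.

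**2. Who knows the arm, by design.**
- Envelope content: the arm (Randomization).
- Who assigns envelopes: study staff other than the evaluating investigator (Randomization).
- Devices: the placebo units are a separate set, and no neutral labelling is described (Study Design).

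Together these mean that the staff who act on the envelope know the allocation. This follows from stated rules, not from silence.

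**3. Who produces the outcomes.**
- Opioid use over 24 and 48 hours: given and charted by the patient's nurse.
- VAS: the patient.
- Other pain scores: nursing and physical therapy.
- Mobility score: an assessor.
- Range of motion: physical therapists, then the clinic.

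Only the evaluating investigator is separated from the envelopes. For the others the protocol neither states masking nor says that they see the allocation.

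**4. What differs between the arms on paper.**
- Common to both: pre-operative titration, the twice-daily two-day session schedule, electrode placement above and below the knee, standard care, and the outcomes recorded.
- Written under the IFC heading only: use of the recorded intensity, the lock, the 30-minute timer, and leaving on or replacing the electrodes.
- Not stated for placebo: how the device is set, how long it runs, and how its sensation relates to the titrated one.

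**5. Size.** The documents give no unblinding rate and no estimate of its effect, so the size cannot be derived. The following is an illustration on assumed values only. Suppose IFC has no effect, but awareness shifts the arm-mean difference by 5% or 10% of 84.2 mg, that is 4.21 or 8.42 mg (one sixth or one third of the 25.26 mg target). With SD 44.7, d = 0.094 or 0.188. With 20 per group, the two-sided t-test at 0.05 has noncentrality d × √(20/2). Rejection probabilities are:

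| Assumed shift | In the direction of the shift | Against it | Total |
|---|---|---|---|
| none | 2.5% | 2.5% | 5.0% |
| 5% | 4.75% | 1.22% | about 6.0% |
| 10% | 8.39% | 0.55% | about 8.9% |

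The shifts have no source in the documents. If there were a real effect, a shift in the opposite direction would help to hide it.

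**The case against.** **Arm-naming envelopes are compatible with a single-blind design.** This stands. They inform staff, not the patient, and do not contradict the label. The remaining weakness is that patient blinding then relies on informed staff giving no cue, with no common script.

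**The plan already has masking measures.** This also stands. The placebo stimulus is aimed at the patient, and the evaluating investigator is kept away from envelope assignment.

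**The difference between the arms can be overstated.** A reader might infer from "This patient specific intensity will be recorded and used for the IFC treatment" that placebo patients do not get their recorded setting. The sentence just before it speaks of each patient's treatment without naming an arm. The VAS text also uses the term IFC treatment loosely, without separating the arms. The lock and timer can be read as general properties of the device. What remains is a gap in the placebo description, not a demonstrated difference in procedure.

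**Patients could compare sensations.** A reader might infer that placebo patients, having felt the titrated signal, will recognise the placebo. The documents do not name the titration device. That it gives the active signal is an inference from the mention of fasciculations and from titration coming before allocation. No mismatch in sensation is shown, and the diminished post-operative sensation mentioned under Risk/Benefit might hide one.

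**The ward nurse may never see the allocation.** Nothing says that she does. Nothing protects against it either.

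**Conclusion.** The point holds in a limited form. Staff who act on the envelope know the arm because the envelope states it and the placebo devices are a separate set with no coding described. The nurses and therapists who generate and record most outcomes are not described as masked. Whether the allocation reaches them or the patient is not shown.

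The size is unknown. The figures of about 6.0% and 8.9% total two-sided error at 20 per group rest wholly on assumed shifts of 5% and 10%, no true effect, and the planning SD. They are not an estimate for this trial and should not be quoted as an inflated error rate. The documents do not support saying that the blind is broken, that the placebo is recognisable, or that the single-blind label is false.

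The change is still worth making, because it alters one stated rule at low cost and removes a source of cues that analysis cannot correct later.

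**What to change.** Keep the pre-operative titration, the existing devices and randomisation after surgery.

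1. The statistician gives each device its own neutral code, so that each arm has several codes and not one shared code.
2. The envelope carries a device code in place of the arm. The statistician holds the key, with sealed copies for emergency unblinding.
3. One written session script serves both arms (set-up, handling of the recorded number, lock, timer, wording to the patient), so that set-up does not reveal the arm.

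Clarifications to add in the same revision: who is blinded; which device is used at titration; how the placebo is set and timed, which is for the sponsor to specify; and how envelopes used in the clinics, with envelope assignment counted as enrolment and randomisation, fit with allocation after surgery.

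Cost: relabelling, new envelope contents, one script, and an amendment if the protocol is already approved. No extra visit is needed. A rule is required for when the coded device is in use by another inpatient, because the number of devices is not stated. If few devices are reused, staff may learn what a code means. Coding does not remove any difference in sensation between active and placebo.

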# **Study Population**

a. The study population will be adult patients older than 18 with severe knee osteoarthritis that have failed non-operative conservative therapy and now require total knee arthroplasty. All patients will undergo unilateral primary total knee arthroplasty with the Zimmer Persona prosthesis performed by [name].

Pre-operative clearance will be done by the Montefiore Geriatrics team prior to day of surgery. Inclusion criteria: Adult patients with knee osteoarthritis who have failed conservative therapy and undergoing elected TKA.

Exclusion criteria:

i. <18 years old

ii. Any patient with pacemaker or any electrical stimulator device

- iii. Significant baseline deformity (flexion contracture)
- iv. Patient with clinically diagnosed fibromyalgia?
- v. Patients without capacity to consent for the study
- vi. Patients not able to have local nerve block or spinal anesthesia
- vii. Patients with prior opioid use

viii. Patient who is categorized to have `Severe` fear and anxiety responses to pain, according to the PCS survey.

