# b. Power/sample size

We will need a sample of 50 subjects in each group to have 80% power to detect a 30% reduction in mean 48 hour opioid use at a two-sided 0.05 significance level, assuming a mean 48 hour opioid use of 84.2mg and a standard deviation of 44.7 in the standard of care group. For this study, we anticipate to start with 25 patients per group.

Drop out/loss to follow up rate: If any patient who is assigned to treatment group decides to leave the study for any reason or any point of the study, they will be dropped out of study. Similarly, if the patient does not show up to post-operative follow up, they will be dropped from the study. The post-op follow up rates are almost at 100%, so we do not anticipate to have more than 10% drop-off. After any potential drop-offs, we aim to have 20 subjects per group at the end of this study.

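### Device sessions have no set hour after surgery, yet the primary outcome is an unadjusted 24 h and 48 h opioid total: a possible loss of sensitivity, of unknown size

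*Combined protocol and SAP*

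**What the plan says.** All references are to the combined protocol and SAP.

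- **Treatment clock, in days.** Study Design states that "both groups will receive IFC treatment (or Placebo treatment) two times a day, for two days during their post-op hospital stay", and that "The study device will be used for only 2 days during the post-surgery hospital stay". On session length: "The device works for 30 minutes at a time". The Randomization section places assignment after surgery, by numbered envelope. No hour is given for opening the envelope, for session 1, or between sessions.
- **Outcome clock, in hours.** The primary outcome "will be the post-operative pain medication usage during the first 24 and 48 hours". On its source: "Daily opioid use will also be accounted based on electronic medical record". Time zero is not defined, although calling the outcome post-operative points to the end of surgery.
- **Analysis.** The Data analysis section compares total opioid per 24 h and 48 h by t-test or Mann-Whitney test. No covariate is named.
- **Sample size.** Power/sample size claims "80% power to detect a 30% reduction in mean 48 hour opioid use" with 50 per group. It then says the study will start with 25 per group and aims for 20 at the end.
- **Context.** The design is described thus: "It will be a prospective, randomized, single-blinded study". One exclusion is "Patients not able to have local nerve block or spinal anesthesia", so every participant can have a block or spinal. The average stay is 48 to 72 hours.

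**The concern.** Nothing ties the two clocks together. If the outcome clock starts at the end of surgery, the hours before session 1 enter both totals although the device has not yet been switched on. Differences between patients in that period are noise for the comparison, and a proportional effect that starts later is diluted when expressed on the whole total. The 24 h total is the more exposed. At the other end, a session delivered after hour 48 cannot act on the outcome that the sample size rests on.

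A second question is whether timing is sure to be equal in the two arms. The envelope names the arm, the study is single-blind, and nothing fixes the interval between opening the envelope and session 1. The plan therefore does not secure equal timing, although it gives no sign that timing would differ.

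**Working it through.** **1. The plan's own figure.** Inputs from Power/sample size: control mean 84.2 mg, SD 44.7, 30% reduction, two-sided 0.05, power 80%.

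- Difference = 0.30 × 84.2 = 25.26 mg, and 25.26 / 44.7 = 0.565 SD.
- n per group = 2 × [44.7 × (1.96 + 0.84) / 25.26]² = 49.16, rounded up to 50. The stated figure reproduces.
- Power at 50 / 25 / 20 per group: 80.7% / 51.5% / 43.1% (normal approximation), or 79.9% / 49.9% / 41.4% (t distribution).

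**2. When the sessions fall.** Assumptions: time zero is the end of surgery, at clock hour H; next-day start; sessions at 09:00 and 17:00. The sessions are then at hours 33−H, 41−H, 57−H and 65−H.

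| Surgery ends | Session 1 | Session 2 | Session 3 | Session 4 |
|---|---|---|---|---|
| 08:00 | 25 | 33 | 49 | 57 |
| 10:00 | 23 | 31 | 47 | 55 |
| 13:00 | 20 | 28 | 44 | 52 |
| 16:00 | 17 | 25 | 41 | 49 |
| 18:00 | 15 | 23 | 39 | 47 |

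Session 4 is after hour 48 whenever H < 17. That is 30 of 4 × 30 = 120 device minutes, or 25%. What that session would have contributed is not modelled.

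With an evening start (20:00, then 09:00, 17:00 and 09:00), session 1 is at 20−H and session 4 at 57−H. For surgery ending at 10:00, 13:00, 16:00 or 18:00, session 1 is at hour 10, 7, 4 or 2 and session 4 at hour 47, 44, 41 or 39.

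**3. Dilution.** Assume a 30% reduction that begins at session 1. Let opioid use up to hour 17 run at k times the later rate, so the 48 h total is proportional to 17k + 31 and the 24 h total to 17k + 7.

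- Session 1 at hour 17: 48 h reduction = 30% × 31/(17k + 31); 24 h reduction = 30% × 7/(17k + 7).
- Session 1 at hour 4: 48 h reduction = 30% × (13k + 31)/(17k + 31).

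| k | 48 h, session 1 at hour 17 | 24 h, session 1 at hour 17 | 48 h, session 1 at hour 4 |
|---|---|---|---|
| 0 | 30% | 30% | 30% |
| 0.5 | 23.5% | 13.5% | 28.5% |
| 1 | 19.4% | 8.75% | 27.5% |
| 2 | 14.3% | 5.1% | 26.3% |

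The 28.5% is an upper bound, because a session given while a block is working may do little.

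**4. Effect on power.** This applies only if the 30% holds after session 1 rather than on the whole total. Let f be the share of control 48 h opioid given before session 1, with difference 25.26 × (1 − f) and SD held at 44.7 (normal approximation).

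| f | n per group for 80% | Power at 50 / 25 / 20 per group |
|---|---|---|
| 0 | 50 | 80.7% / 51.5% / 43.1% |
| 0.1 | 61 | 72.0% / 43.6% / 36.3% |
| 0.2 | 77 | 61.8% / 35.9% / 29.8% |
| 0.3 | 101 | 50.7% / 28.7% / 23.9% |

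The documents do not give f.

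**5. What adjustment could recover.** Let p be the share of the mean total before session 1, with equal coefficients of variation before and after, and correlation r between the two periods (assumed). The share of the variance of the 48 h total left after adjustment is (1−p)²(1−r²) / [p² + (1−p)² + 2rp(1−p)].

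| Case | p | r = 0 | r = 0.5 |
|---|---|---|---|
| Session 1 at hour 17, even use | 17/48 | 77% | 41% |
| Session 1 at hour 17, half rate before | 8.5/39.5 | 93% | 56% |
| Session 1 at hour 4, even use | 4/48 | 99% | 68% |

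If nobody uses opioid before session 1, there is no gain.

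**The case against.** Total post-operative opioid is a legitimate and clinically relevant outcome, and an unadjusted randomised comparison of it is valid. The sample size section defines its 30% on mean 48 h use, so the direct reading is a net effect on the whole total; planned power at 50 per group then stands. Participants must be able to have a block or spinal, which makes heavy early opioid use less likely. A session 4 after hour 48 depends on a next-day start and on clock times that the protocol does not state; same-day treatment or closer spacing is equally permitted. Earlier sessions also carry a safety cost: the Risk/Benefit section cites burns and insensate skin, and its safeguard on intensity speaks only of slightly diminished sensation.

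All of this stands. It limits the size of the point and rules out a mandatory early session. It does not supply a time zero, a timetable or a use for the pre-assignment opioid data.

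A reader might go further and infer that the comparison is biased. The documents do not support that. Both arms have the same regimen, the surgeon and study group are kept out of the randomisation process, and the investigator who evaluates patients after surgery does not assign envelopes. Arm-dependent timing is possible because nothing prevents it, but nothing shows that it would occur. Nor do the documents show that a large part of the effect must be lost, or that session 4 will generally miss the window.

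**Conclusion.** The point holds as a loss of sensitivity, not as a bias when timing is equal in both arms. That the hours are unset and the analysis unadjusted can be read directly from the plan. The size cannot: under the assumed clock times and opioid rates, a 30% effect from session 1 at hour 17 becomes anything from 30% down to 14.3% at 48 h. The low-loss end is plausible given the required block or spinal. If the planned 30% is already net, the dilution and power tables show only what earlier sessions could gain.

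A reader might take the reproduced 80% as reassurance about this trial. It is not, because it belongs to 50 per group, and the numbers actually planned leave roughly a coin toss or less before any dilution. There is little sensitivity to give away, so cheap ways of recovering some are worth taking.

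**What to change.** 1. **Data analysis.** Analyse the 48 h total with a linear model containing arm and the opioid given between end of surgery and assignment, on ranks if skewed. Assignment cannot affect this covariate, so the adjustment is valid. Cost: one degree of freedom. No new data are needed, because the 24 h and 48 h totals already require dose times.
2. **Randomization.** Open the envelope at the hospital immediately before session 1, so that neither the start time nor the covariate can depend on arm. Cost: envelopes and existing study staff must be available at the hospital, whereas the plan now has the envelopes used in the study clinics.
3. **Study Design.** Set time zero at the end of surgery. Use one timetable for both arms with all four sessions before hour 48 where safe. Replace the limit of two days of device use with a limit of 48 hours from surgery, since an evening start touches three calendar days. Record each session's start time, which can be noted at the VAS rating already taken before treatment, and report by arm how many sessions fell after hour 48. Cost: protocol wording, tighter scheduling and four recorded times per patient.
4. **Safety limit.** Do not require a same-day start. Allow it only once sensation at the electrode sites has returned; otherwise start the next morning and keep the patient in the analysis. Cost: a sensation check, and some deferred patients may still have session 4 after hour 48.

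None of this needs extra patients, and none of it repairs the shortfall from 50 per group.
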